6.1.4 Definitions

6.1.4.1 Baseline (Core)

For de novo subjects, the baseline (core) is undefined. For other subjects, the baseline (core) is defined as follows.

For effectiveness endpoints (excluding seizure), the baseline (core) will be defined dependent on their core study. For subjects from ZX008-1501, ZX008-1502, or ZX008-1504 Cohort 2, baseline (core) is the last value prior to randomization in the preceding double-blind study. For subjects from ZX008-1504 Cohort 1, baseline (core) is the last value prior to the start of PK dosing and assessments. For De Novo subjects, the baseline is the last value prior to dosing in ZX008-1503.

For all subjects in Study ZX008-1501, Study ZX008-1502, or Study ZX008-1504 Cohort 2, the baseline (core) period is equivalent to the core study pre-randomization period, i.e., the approximately 42-day span just prior to randomization and start of treatment in the core study. The baseline (core) seizure frequency will be based on the information collected from their daily diaries during the baseline period (lasting approximately 42 days).

For subjects from Study ZX008-1504 Cohort 1 the baseline (core) for efficacy rating scales (e.g. questionnaires) will be the last rating prior to start of dosing in the Core Study. Baseline seizure frequency for Study ZX008-1504 Cohort 1 will not be calculated.

6.1.4.2 *Baseline (OLE)*

Baseline (OLE) value for the Open-label treatment period is defined as the last assessment on or before the start of the OLE period. In most cases, (though not seizure frequency) this will be the value obtained at Visit 1 (Study Day 1) of Study ZX008-1503.

Thus, Baseline (OLE) lab, vital signs, ECG, ECHO, assessments refer to the assessments obtained on this day, as does Baseline (OLE) value for effectiveness endpoints with the exception of seizures.

For de novo subjects, the baseline (OLE) seizure frequency will be based on the information collected from their daily diaries during the baseline period (lasting approximately 28 days) prior to first dose in ZX008-1503.

6.1.4.3 *Open-Label Extension (OLE) Treatment Period*

The OLE Treatment Period covers the 36 months during which subjects will receive open label treatment with ZX008.

For each subject, OLE day 1 (OLED1) is the subject's first day of dosing in the OLE period. Study day for 1503 begins with OLED1.

6.1.4.4 *Post-dosing Period*

The Post-dosing Period begins immediately at the end of OLE Treatment Period and extends for 2 weeks.

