6.1.4.5 *Follow-up Period*

Subjects are to return for an ECHO and ECG assessment 3 and 6 months after the end of the study. The follow-up period begins the day after Visit13 and ends with Visit15.

6.1.5 *Other Definitions*

6.1.5.1 *Phase and Study Day Definitions*

The analyses will require definition of 3 Phases: Pre-OLE, OLE, and Post-OLE.

- The pre-OLE Phase comprises (1) the baseline (Core) period, (2) the Core Study (CS) period (including the transition period in the core study)
- The OLE Phase starts from dosing on OLED1 and comprises (1) the OLE Treatment Period, and (2) the Taper Period. The last day of the OLE phase is the date of Visit 17.
- The post-OLE phase begins one day after the date of Visit 17 in 1503 and ends with the date of Visit 19.

Study Day 1 is the date of first dose in the OLE Study. In most cases, this will be the date of Visit 1 or the day after that date.

6.1.6 *Visit Windows and Period Start/Stop Dates*

The following definitions of phase and period will be used:

Table 6. Definition of Phase/Period

Phase	Period	Description
Pre-OLE Phase	Baseline (Core) Period	This description here applies to all subjects except the de novo subjects. This period refers to the period prior to the beginning of the double-blind period in the Core study. The Baseline (Core) period start date is the date of Visit 1 in the Core study. The Baseline (Core) period end date is the date of Visit 3/randomization in the Core study. For subjects in Study ZX008-1504 (Cohort 1), the baseline period starts and ends on the date of Visit 1.
Pre-OLE Phase	Core Study Period	This description here applies to all subjects except the de novo subjects. The start date of this period is the date of randomization or first dose in the Core (double-blind) study, whichever occurs first. The end date of this period is the last date the subject was on study treatment. For subjects entering Study ZX008-1503 who completed Core studies ZX008-1501, ZX008-1502 or ZX008-1504 Cohort 2, this will be the date of Visit 13 in the core study. For subjects who discontinue early from the Core study, the Core study period end date is the latest assessment date for that study. For subjects entering ZX008-1503 who were in ZX008-1504 Cohort 1, this will be the date of the Visit 17 assessment in Study 1504 Cohort 1 (for those who completed), or the date of the latest assessment date (for those who discontinued ZX008-1504 Cohort 1 prematurely but were allowed entry into 1503, if any).

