Pre-OLE Phase	Baseline (OLE) Period – de novo subjects	This description here applies to the de novo subjects. This start date of this period be the date of screening. The end date of the period will be the last date prior to the first dose of study drug in Study ZX008-1503.
OLE Phase	OLE Treatment Period	The OLE Treatment Period consists of the 36-month period from Visit 1 of the OLE study through Visit 16 of the OLE study The OLE Treatment Period start date is the date of first dose in Study ZX008-1503. The OLE Treatment Period end date is the date of end of study visit, Visit 16/ET. For subjects who discontinue early from the study, the OLE Treatment Period end date will be the date of the ET visit - safety measures collected at the last clinic visit will be used even in the event that study drug was discontinued prior to the date of the visit. Note: Adverse events occurring up to Visit 17 are regarded as occurring during treatment. In addition, AEs occurring up to 30 days after the last dose date will be regarding as treatment emergent.
OLE Phase	Taper Period	The Taper period consists of 2 weeks starting from end of study/early termination visit (Visit 16) + 1 day. The end date of this period is the date recorded for Visit 17.
Post-OLE Phase	Post-OLE Period	The start date of the post-OLE period is the date of Visit 17, + 1 day for subjects who complete the OLE Treatment period, or the day after the date of end of taper, for subjects who discontinue early. [There is not explicit end date for the post-OLE Phase. However, if needed, this may be set to be 45 days after the date of Visit 19, or V17 date + 210.]

For the purpose of statistical analysis, visit windows around the target visit dates will be implemented to capture effectiveness and/or safety data within similar periods. These windows are distinct from the

permissible visit scheduling windows specified in the Visit Schedule in the protocol that are used for the conduct of the study.

The following rules will be used to window data into treatment periods for tabulations that are generated by time during the OLE Treatment period.

Table 7a. Time Intervals for Analysis Visits for Seizure Analysis*

Analysis Phase/Period	Scheduled Visit Number in ZX008-1503	Analysis Visit**	Time Interval (label on output)	Time Interval (Day)
Pre-OLE	N/A	-99	Baseline (Core)*	Core Study Day -42 to Day-1 of Core Study
Pre-OLE	N/A	-9	Core Study (T+M)*	Day 1 of Core Study to End of T+M in Core Study

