TEAEs starting in the 3rd month of OLE by System Organ Class, Preferred Term and Prior Treatment in Feeder Study
Safety Population

Table 14.3.1.9.4.1
TEAEs starting in the 3rd month of OLE by System Organ Class, Preferred Term and Prior Treatment in Feeder Study
Safety Population (Japan)

Table 14.3.1.10.1
 Treatment-Emergent Adverse Events that Occurred in at least 5% of Subjects during Double-blind Treatment Period by MedDRA System Organ Class and Preferred Term
 with Mean Time to Onset (days) and Mean Duration (days)
 Safety Population

MedDRA System Organ Class and Preferred Term	Placebo (N=xx) n (%) / Mean Onset/ Mean Duration	ZX008 0.2 mg/kg/day (N=xx) n (%) / Mean Onset/ Mean Duration	ZX008 0.5 mg/kg/day (N=xx) n (%) / Mean Onset/ Mean Duration	ZX008 0.8 mg/kg/day (N=xx) n (%) / Mean Onset/ Mean Duration	Any DB ZX008 (N=xx) n (%) / Mean Onset/ Mean Duration
Subjects with any TEAE starting in the first month.	XX (XX.X%) / xx.x /xx.x	XX (XX.X%) / xx.x /xx.x	XX (XX.X%) / xx.x /xx.x	XX (XX.X%) / xx.x /xx.x	XX (XX.X%) / xx.x /xx.x
System Organ Class 1	XX (XX.X%) / xx.x /xx.x	XX (XX.X%) / xx.x /xx.x	XX (XX.X%) / xx.x /xx.x	XX (XX.X%) / xx.x /xx.x	XX (XX.X%) / xx.x /xx.x
Preferred Term 1	XX (XX.X%) / xx.x /xx.x	XX (XX.X%) / xx.x /xx.x	XX (XX.X%) / xx.x /xx.x	XX (XX.X%) / xx.x /xx.x	XX (XX.X%) / xx.x /xx.x
Preferred Term 2	XX (XX.X%) / xx.x /xx.x	XX (XX.X%) / xx.x /xx.x	XX (XX.X%) / xx.x /xx.x	XX (XX.X%) / xx.x /xx.x	XX (XX.X%) / xx.x /xx.x

TEAE = Treatment-Emergent Adverse Event.

TEAE = Treatment-Emergent Adverse Event.

Note: Percentages are calculated based on the number of subjects in each treatment group.

Note: Mean Onset and Mean Duration are measured in days. The onset day is the study day at the adverse event onset. The duration is the number of days from onset to resolution or from onset to last follow-up day if the event was ongoing.

Note: Adverse events are classified as treatment-emergent if they started on or after the date of first dose of study treatment. Adverse events with partial or missing start dates are classified as treatment-emergent, unless the non-missing components of the start date confirm otherwise.

Note: In subjects with more than one occurrence of the same event, the time to onset and duration is based on the earliest occurring event.

Note: Time to onset is the number of days since first treatment with either ZX008 or placebo. The duration of an event is limited to the period of the double-blind study.

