Note: A subject with more than one TEAE with the same preferred term is counted once for that term. A subject with more than one TEAE under a system organ class is counted once for that class.

Programming note: Use shell for 14.3.1.10.1 for 14.3.1.10.1.1

Table 14.3.1.10.1.1
 Treatment-Emergent Adverse Events that Occurred in at least 5% of Subjects during Double-blind Treatment Period by MedDRA System Organ Class and Preferred Term
 with Mean Time to Onset (days) and Mean Duration (days)
 Safety Population (Japan)

Table 14.3.1.10.2
 Treatment-Emergent Adverse Events that Occurred in at least 5% of Subjects during Double-blind through Open-label Treatment Periods by MedDRA System Organ Class and Preferred Term, Mean Average Dose in ZX008-1503 with Mean Time to Onset (days) and Mean Duration (days)
 Safety Population

MedDRA System Organ Class and Preferred Term	ZX008 0 - < 0.2 mg/kg [1] (N=xx) n (%) / Mean Onset/ Mean Duration	ZX008 0.2 - < 0.4 mg/kg (N=xx) n (%) / Mean Onset/ Mean Duration	ZX008 0.4 - < 0.6 mg/kg (N=xx) n (%) / Mean Onset/ Mean Duration	ZX008 0.6 - < 0.8 mg/kg (N=xx) n (%) / Mean Onset/ Mean Duration	Any OLE ZX008 (N=xx) n (%) / Mean Onset/ Mean Duration
	Subjects with any TEAE starting in the first month.	XX (XX.X%) / xx.x /xx.x	XX (XX.X%) / xx.x /xx.x	XX (XX.X%) / xx.x /xx.x	XX (XX.X%) / xx.x /xx.x
System Organ Class 1	XX (XX.X%) / xx.x /xx.x	XX (XX.X%) / xx.x /xx.x	XX (XX.X%) / xx.x /xx.x	XX (XX.X%) / xx.x /xx.x	XX (XX.X%) / xx.x /xx.x
Preferred Term 1	XX (XX.X%) / xx.x /xx.x	XX (XX.X%) / xx.x /xx.x	XX (XX.X%) / xx.x /xx.x	XX (XX.X%) / xx.x /xx.x	XX (XX.X%) / xx.x /xx.x
Preferred Term 2	XX (XX.X%) / xx.x /xx.x	XX (XX.X%) / xx.x /xx.x	XX (XX.X%) / xx.x /xx.x	XX (XX.X%) / xx.x /xx.x	XX (XX.X%) / xx.x /xx.x

TEAE = Treatment-Emergent Adverse Event.

Note: Percentages are calculated based on the number of subjects in each treatment group.

Note: Mean Onset and Mean Duration are measured in days. The onset day is the study day at the adverse event onset. The duration is the number of days from onset to resolution or from onset to last follow-up day if the event was ongoing.

Note: Adverse events are classified as treatment-emergent if they started on or after the date of first dose of study treatment. Adverse events with partial or missing start dates are classified as treatment-emergent, unless the non-missing components of the start date confirm otherwise.

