Note: In subjects with more than one occurrence of the same event, the time to onset and duration is based on the earliest occurring event.

Note: Onset day is measured from the first date of ZX008 treatment to onset. Duration for the TEAEs in the placebo group start after the subject starts ZX008 treatment in the OLE.

[1] For subjects treated with Placebo in the core study, TEAEs are counted only after the subject started ZX008 treatment.

Programming note: Use the shell for Table 14.3.1.10.2.1.

Table 14.3.1.10.2.1

Treatment-Emergent Adverse Events that Occurred in at least 5% of Subjects during Double-blind through Open-label Treatment Periods by MedDRA System Organ Class and Preferred Term, Mean Average Dose in ZX008-1503 with Mean Time to Onset (days) and Mean Duration (days)
 Safety Population (Japan)

Programming Notes: Use the Listing 16.2.7.1 shell for the following tables.

Table 14.3.2.1
Listing of Deaths

Table 14.3.2.1.1
Listing of Deaths (Japan)

Table 14.3.2.2
Listing of SAEs

Table 14.3.2.2.1
Listing of SAEs (Japan)

Table 14.3.2.3
Listing of Discontinuations Due to AE

Table 14.3.2.3.1
Listing of Discontinuations Due to AE (Japan)

Laboratory Data

Please see below (also in SAP) for time windows

Time Intervals for Analysis Visits for Laboratory Data and Vital Signs

Analysis Phase/Period	Scheduled Visit Number in ZX008-1503	Analysis Visit Number*	Time Interval (label on output)	Time Interval (Day)	Target Time Point (Day)
Pre-OLE	1	1	Baseline (OLE)	1	1
OLE	2	2	Week 2 (OLE)	2 to 20	15
OLE	3	3	Month 1 (OLE)	21 to 44	30
OLE	4	4	Month 2 (OLE)	45 to 74	60
OLE	5	5	Month 3 (OLE)	75 to 134	90
OLE	6	6	Month 6 (OLE)	135 to 224	180
OLE	7	7	Month 9 (OLE)	225 to 314	270
OLE	8	8	Month 12 (OLE)	315 to 409	365
OLE	9	9	Month 15 (OLE)	410 to 499	455
OLE	10	10	Month 18 (OLE)	500 to 589	545
OLE	11	11	Month 21 (OLE)	590 to 679	635
OLE	12	12	Month 24 (OLE)	680 to 774	730
OLE	13	13	Month 27 (OLE)	775 to 864	820
OLE	14	14	Month 30 (OLE)	865 to 954	910
OLE	15	15	Month 33 (OLE)	955 to 1044	1000
OLE	16	16	Month 36 (OLE)	1045 to 1109	1095
OLE	OLE last Visit**	99	Last Value	Day 2 to Visit 17 date	

Programming Notes:

*For multiple measurements within a time window, please use the closest to the target time point. Note that measurements occurring on the end date of a phase/period or start date of a new phase/period are assigned to the preceding phase/period. For example, measurements taken on OLE Study Day1 are assigned as Baseline (OLE).

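### Shell Tables 14.3.1.10.1 and 14.3.1.10.2 restrict their any-TEAE row to the first month, and 14.3.1.10.2 counts onset day from two different dates

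*SAP*

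**What the plan says.** The shells are Tables 14.3.1.10.1 and 14.3.1.10.2. Their Japan copies, 14.3.1.10.1.1 and 14.3.1.10.2.1, reuse them.

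- **Period.** The first table's title is "Treatment-Emergent Adverse Events that Occurred in at least 5% of Subjects during Double-blind Treatment Period", by class and preferred term, with mean time to onset and mean duration. The second title extends the period through open-label treatment.
- **First row.** In both it is "Subjects with any TEAE starting in the first month". The same label heads Table 14.3.1.9.2, where a programming note restricts events to open-label Days 1 to 30.
- **Onset, common note.** Both shells state "The onset day is the study day at the adverse event onset".
- **Onset, table-specific note.** Table 14.3.1.10.1 adds "Time to onset is the number of days since first treatment with either ZX008 or placebo". Table 14.3.1.10.2 adds "Onset day is measured from the first date of ZX008 treatment to onset".
- **Study day.** Section 6.1.4.3 has "Study day for 1503 begins with OLED1" and Section 6.1.5.1 has "Study Day 1 is the date of first dose in the OLE Study". Where the SAP means the core clock it says so, as in Table 7a: "Core Study Day -42 to Day-1 of Core Study".

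**The concern.** The first row does not match the table it heads. It is limited to one month, while the class and preferred-term rows below it have no such limit and the titles span months or years. A reader takes the top row as the overall count, so it must be at least as large as every row under it. As labelled, it need not be.

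Mean onset is one of the three quantities in every cell. In 14.3.1.10.2 its definition is given twice with different origins, and nothing says which governs. The table covers both studies. If the study-day definition is programmed, events from the core study carry negative values and are averaged with positive values from the extension. The columns are open-label mean-dose groups, so each can mix former placebo and former ZX008 subjects. The error would then differ from column to column and could not be removed afterwards by a constant.

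**Working it through.** The SAP gives no figure to reproduce here, so the check is date arithmetic.

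**Inputs**
- Core treatment: 14 weeks = 14 × 7 = 98 days (Section 3.1).
- Transition between core Visits 12 and 13: *g* days, length not stated in the SAP. I assume 0 to 30, the upper end taken from the Day -30 to Day -1 window that shell Table 14.3.1.9.1 uses for that interval. The 14 weeks are taken to exclude it.
- Open-label period: up to Day 1095 (Table 7a).
- Approximate roll-over numbers (Section 3.2, Table 1): 200 from active double-blind arms, 120 from placebo, 320 in all.
- First-dose date counted as Day 1 with no Day 0, as Table 7a implies.

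**Onset in 14.3.1.10.2, subjects on ZX008 in a double-blind study**

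Open-label Day 1 is core day 98 + *g* + 1.
- An event on core day *d* has 1503 study day *d* − 1 − (98 + *g*), and day *d* from first ZX008.
- An event on open-label day *k* has study day *k*, and day 98 + *g* + *k* from first ZX008.

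Illustration (invented onsets): half the first events on core day 20, half on open-label day 60.

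| *g* | Study-day values | Mean | From first ZX008 | Mean |
|---|---|---|---|---|
| 0 | −79, 60 | −9.5 | 20, 158 | 89.0 |
| 30 | −109, 60 | −24.5 | 20, 188 | 104.0 |

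The origins are 98 days apart with no transition and 128 with 30 days.

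**Subjects on placebo in the core study.** Under Section 3.2 their first ZX008 dose comes in the transition, so the origins differ by at most *g*, that is 0 to 30 days under the assumption.

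**Average over the 320**, if each contributed equally: (200 × 98 + 120 × 0) / 320 = 61.25 days at *g* = 0, and (200 × 128 + 120 × 30) / 320 = 91.25 days at *g* = 30.

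**Onset in 14.3.1.10.1.** Read literally on the 1503 clock with *g* = 0, core day 1 becomes −98, day 50 becomes −49 and day 98 becomes −1. Read on the core clock, study day and days since first treatment differ by at most one day (Day 1 against 0).

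**First row.** Thirty days is 30/98 = 30.6% of the double-blind period and 30/(98 + 1095) = 2.5% of double-blind plus open-label. These are shares of time, not of events. To see what they might mean for a count, assume a constant hazard over 98 days, so that first-month proportion = 1 − (1 − *p*)^(30/98):
- *p* = 30% gives 10%.
- *p* = 60% gives 24%.
- *p* = 90% gives 51%.

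If events cluster early the shortfall is smaller. If the label keeps its Table 14.3.1.9.2 meaning (open-label Days 1 to 30), the row in 14.3.1.10.1 would hold no double-blind event at all.

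**The case against.** The best defence is that each table already names its clock in a later, specific note, and that the study-day sentence is boilerplate carried into both shells. For 14.3.1.10.1 this largely stands. The columns are the double-blind arms, and duration is confined to the double-blind study. Treatment emergence requires onset on or after first dose of study treatment; if that were the 1503 dose, the table would be empty. The definition in Section 6.1.4.3 is also expressly for 1503. A reader might infer that this table will report negative mean onsets, but its own structure does not support that. What remains is a literal conflict between two notes.

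The defence is weaker for 14.3.1.10.2. That table spans both studies, so context cannot choose the clock, and its two notes define the same term differently.

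It can also be said that the first-month label is a copying slip without the Day 1 to 30 programming note found in 14.3.1.9.2, and that a total below one of its components would be caught in checking. That may be so, but nothing in either shell corrects the label.

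A reader might further infer that adverse-event incidence is understated. It is not, beyond this one row: class and preferred-term counts stand, and Tables 14.3.1.1 and 14.3.1.2.1 report open-label any-TEAE incidence without a month limit.

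Finally, the tables are descriptive and Section 6.4.1.2 does not list time to onset among its summaries. In Appendix 1 the general versions are marked for neither the interim nor the 120-day report. They are nevertheless listed for the final report, and the Japan copies are marked for the 2020 Japan report.

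**Conclusion.** The point holds at minor severity. The first row of both tables contradicts the title, and as written it would omit later events. How far it would fall short cannot be derived from the SAP; the constant-hazard figures are illustration only.

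In 14.3.1.10.2 mean onset is ambiguous by at least 98 days for subjects who took ZX008 in a double-blind study. This rests on 14 weeks of core treatment plus a transition of unstated length, and becomes 98 to 128 days if the transition is 0 to 30 days. It would be wrong to apply that shift to everyone: for core-placebo subjects, about 120 of 320, the difference is at most the transition. In 14.3.1.10.1 the fault is loose wording that invites a literal misreading. The primary safety conclusion is not affected.

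**What to change.** In both shells, and so in the Japan copies:

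1. Delete the sentence that equates onset day with study day.
2. Keep one origin per table: first double-blind treatment (ZX008 or placebo) for 14.3.1.10.1, and first ZX008 dose, whether in the core study or the extension, for 14.3.1.10.2.
3. State one day-count convention for both tables. The existing note in 14.3.1.10.1 implies day 0 on the first-dose date. Day 1 would serve equally well but changes that note, so the choice should be explicit.
4. Relabel and program the first row as subjects with any TEAE over the table's own period.

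The cost is a few lines of shell text and one derived onset variable per table. No new data are needed.

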3.2 TREATMENTS

Subjects in the double-blind studies Z008-1501, -1502, and cohort 2 of 1504 who enter Study ZX008-1503 would have transitioned to 0.2 mg/kg during the transition period (between Visits 12 and 13), as described in the 1501 and 1502 Clinical Study Protocols Section 5.5.5, and 1504 Sections 5.5.6 and 5.5.7. Subjects entering from Cohort 1 in Study ZX008-1504 will enter a transition period at a fixed dose of ZX008 0.2 mg/kg/day for up to 24 additional weeks.

In Study ZX008-1503, during the OLE Treatment Period, all subjects will be treated initially with 0.2 mg/kg/day for 1 month to assess effectiveness of this dose in all study subjects. After 1 month at a dose of 0.2 mg/kg/day, the investigator may adjust the dose of each subject based on effectiveness and tolerability. Subjects whose condition worsened relative to their status at the end of the double-blind feeder study could request permission to increase to 0.4 mg/kg/day (max 30mg) after approximately 2 weeks on the 0.2 mg/kg dose. Dose changes should be made in increments of 0.2 mg/kg/day, to a maximum of 0.8 mg/kg/day but not to exceed total dose of 30 mg/day. Dose increases should not occur earlier than every 14 days at each dose level. For subjects in Study ZX008-1504 Cohort 2, the dose titration schedule is 0.2 mg/kg/day, to 0.4, to 0.5 not to exceed 20 mg/day. Dose increases may only occur after a review of the diary and reported AEs, and if, in the investigator's opinion, seizure frequency, severity, and/or duration indicates a change in medication regimen is warranted. Dose decreases for tolerability can occur at the investigator's discretion, in dose amounts and frequency appropriate for the situation. ZX008 dose adjustments outside of these parameters should be discussed with the Medical Monitor prior to initiation.

Effectiveness and safety data will be provided for all subjects treated with ZX008. Data will be summarized by subjects' treatment group in their previous study.

The treatment groups that may be used to summarize the results of the final analysis are presented in Table 1. Groups 1 to 5 are the basic treatment groups.

Table 1. Treatment Groups in Study ZX008-1503 According to Treatment in Feeder Study

Name of Treatment Group	Treatment Group Code	AED Treatment from Feeder study	Feeder Study(s)	Approximate Total Number of subjects at Final Analysis

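### Tables 14.3.1.10.2 and 14.3.1.10.2.1 include adverse events from the core study but classify them only by mean dose in ZX008-1503, so an event can be counted under a dose at which it did not occur

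*SAP*

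**What the plan says.** The shell for Table 14.3.1.10.2 in the SAP's appendix covers events "during Double-blind through Open-label Treatment Periods by MedDRA System Organ Class and Preferred Term, Mean Average Dose in ZX008-1503". Its columns are four bins of mean dose in 1503 (0 to <0.2, 0.2 to <0.4, 0.4 to <0.6 and 0.6 to <0.8 mg/kg) plus one column for any open-label dose. No column carries the core-study dose.

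The notes confirm that core-study events are meant to be in the table:
- "Onset day is measured from the first date of ZX008 treatment to onset", which for an active core arm means the core study.
- When a term recurs in a subject, "the time to onset and duration is based on the earliest occurring event".
- The only exclusion is note [1]: "For subjects treated with Placebo in the core study, TEAEs are counted only after the subject started ZX008 treatment".

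Table 14.3.1.10.2.1 is the same shell for Japan. The output list marks it for the 2020 Japan report. SAP section 1 plans that analysis for when every Japanese subject has reached at least Month 3.

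On dosing, SAP section 3.2 has all subjects start 1503 at 0.2 mg/kg/day for a month, with increases at least 14 days apart. It adds that "Dose decreases for tolerability can occur at the investigator's discretion, in dose amounts and frequency appropriate for the situation".

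**The concern.** The numerator and the classifier refer to different periods. An event that began on a core dose of 0.2, 0.5 or 0.8 is counted under an average formed only from later 1503 dosing. The earliest-occurrence rule makes the mismatch explicit: if a term occurs in both studies, the core occurrence supplies onset and duration while 1503 supplies the dose. The average is also fixed after the event, and may be lower because of it where the dose was reduced for tolerability.

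In the output list this pair are the only adverse-event tables with columns for dose in 1503. A reader looking for adverse events by dose in the extension will go to them, and the counts do not mean what the column heads suggest.

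**Working it through.** The SAP states no figure to reproduce here. The check is where the shell puts a core-onset event, using the SAP's own dosing steps.

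**Inputs.** Start at 0.2 for 30 days; then at least 14 days per step; steps of 0.2 up to 0.8, or 0.4 then 0.5 with stiripentol (sections 3.2 and 3.3.1). An early move to 0.4 after about two weeks is possible on request (section 3.2). Mean daily dose is taken over the subject's whole 1503 treatment, as defined in the mean-dose exposure shell (14.1.5.8.1). Assumed: fastest permitted titration, no reductions, no effect of the 30 mg or 20 mg caps.

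**Formula.** Mean dose at day T = sum of (days × dose) / T.

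**Core 0.8, returned to 0.8**
- Day 90: (30×0.2 + 14×0.4 + 14×0.6 + 32×0.8)/90 = 45.6/90 = 0.507, column 0.4 to <0.6.
- With the early step: (14×0.2 + 14×0.4 + 14×0.6 + 48×0.8)/90 = 55.2/90 = 0.613, column 0.6 to <0.8.
- Standard steps, reaching 0.6: 20 + 0.8(T − 58) = 0.6T gives T = 132 days. At day 1095 the mean is 849.6/1095 = 0.776.

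**Core 0.8, held at 0.4 in 1503**
- Day 90: (6 + 60×0.4)/90 = 0.333. Day 1095: (6 + 1065×0.4)/1095 = 0.395. Both fall in 0.2 to <0.4.

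**Core 0.5, returned to 0.5**
- Day 90: (6 + 5.6 + 46×0.5)/90 = 34.6/90 = 0.384, column 0.2 to <0.4.
- Reaching 0.4: 11.6 + 0.5(T − 44) = 0.4T gives T = 104 days. Day 1095: 0.491, column 0.4 to <0.6.

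**Core 0.2, raised to 0.8**
- Same path as the first case: 0.653 at day 180 and 0.776 at day 1095. An event that began on 0.2 is counted in 0.6 to <0.8.

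**Core 0.2, kept on 0.2**
- Mean 0.2, column 0.2 to <0.4. Not misplaced.

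**Subjects exposed (SAP Table 1, approximate).** Groups 2 to 4: 80 + 80 + 40 = 200 of 320 double-blind rollovers (62.5%). On 0.5 or 0.8: 40 + 80 = 120.

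**Bin edges.** This shell closes its bins on the left; exposure tables 14.1.5.8.1 and 14.1.5.1.10.1 close theirs on the right. A subject kept on 0.2 is in 0.2 to <0.4 here but in >0 to 0.2 there.

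**The case against.** The strongest reply is that core events are already shown against the core dose. Table 14.3.1.10.1 tabulates double-blind events by arm, with duration limited to the double-blind study. The main open-label tables (14.3.1.1, 14.3.1.2.1, 14.3.1.6) use feeder-group columns and are untouched. Section 6.4.1.2 lists no adverse-event-by-dose summary and rules out p-values. The main version of this shell is not marked for the interim or the 120-day update. On that view, a footnote saying that the columns are not dose at onset would be enough.

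The point about weight stands: no principal safety table depends on this shell. The rest does not remove the problem. Table 14.3.1.10.1 covers only the double-blind period and leaves the combined counts as they are. A footnote would warn the reader but still leave events in the wrong columns.

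Some stronger readings are not supported:
- A reader might infer that the table systematically moves high-dose events into low-dose columns. The worked cases run in both directions.
- A reader might take 200 or 120 as the number misplaced. A core 0.8 subject back on 0.8 ends in the right column, and the SAP gives no event counts.
- A reader might object that core-placebo subjects are counted only from first ZX008. That applies one clock, time since first ZX008, to everyone.
- A reader might conclude that the columns cannot be compared with the exposure tables. The cut points are the same; only means lying exactly on a boundary change class.

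**Conclusion.** The point holds. Programmed as written, Tables 14.3.1.10.2 and 14.3.1.10.2.1 can count core-onset events from active-arm subjects under a dose, higher or lower, at which they did not occur, and pair core-study timing with a 1503 dose.

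About 200 subjects are exposed, taking Table 1's approximate numbers. How many events move cannot be derived from the SAP. For subjects titrated back to their core dose the shift is largest at an early cut and disappears with follow-up (after day 132 for 0.8 and day 104 for 0.5, under the stated assumptions). This makes the Japan table the more affected, although Month 3 is a minimum and some subjects will have longer follow-up. For subjects who settle on a dose different from their core dose, the misplacement persists to the end.

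This is a defect in one descriptive shell and its copy. It does not undermine the safety analysis as a whole.

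**What to change.** Choose one of two definitions for both tables:

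1. Keep the mean-1503-dose columns and include only events with onset on or after OLE Day 1. Core events stay in Table 14.3.1.10.1, and those starting between feeder Visits 12 and 13 already have Table 14.3.1.9.1. This is the smaller change, but onset is no longer described from first ZX008 exposure. The column can still reflect dosing after the event, which a footnote should say.
2. Keep the combined window and assign each event to the dose in force on its onset date: the core dose for core onsets, the assigned 1503 dose for OLE onsets. Use exposure time at that dose as the denominator. A subject may then appear in more than one dose column, which the notes should state.

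As a secondary change, use the exposure tables' interval closure with an open top class: >0 to 0.2, >0.2 to 0.4, >0.4 to 0.6, >0.6. Under the second option the open top class is needed, because an event at an assigned 0.8 has no place in a class ending below 0.8.

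The cost is shell text and programming. Onset dates and assigned doses are already required for Listing 16.2.7.1 and Table 14.1.5.1.7.1; core-study dose is known from the feeder-study arm.
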